APPENDIX 3: ADJUDICATION OF OUTCOMES

Primary outcome:

An independent Committee will adjudicate, for each patient, whether he or she has reached the endpoint. In the absence of follow-up imaging, the committee will adjudicate other potential cases of treatment failures (expected to be rare) such as:

- Hemorrhage during the follow-up period
- Retreatment of the same lesion by endovascular or surgical means during the follow-up period
- Occurrence or progression of a mass effect in relation to the treated aneurysm
- Morbidity and mortality that precludes follow-up

The pilot phase of the study was powered to detect a difference of 3% in mean packing density between the 2 groups. This will be measured by the Core lab. For both types of treatment, the packing density (PD) will be calculated as the volume of coils (VC) over the volume of the aneurysm (VA): PD = VC/VA with VA = $(4/3)\pi(length/2)(width/2)^2$

Safety

A. Safety data

Safety endpoints

- Mortality
- Morbidity (mRS ≥ 3)
- Combined Mortality & Morbidity(M&M) (mRS ≥ 3 at 12 months)
- Serious Adverse Event

Endpoint assessment

- For all DELTA patients
- Separately for ruptured and unruptured DELTA patients

Causality attribution

- Treatment-related
- Strictly treatment related: any M&M associated with a procedural event or complication or hemorrage
- Possibly related: any M&M occurring within 30 days
- Not treatment related (> 30 days)
- Related to aneurysm
- Unrelated

Safety data will be adjudicated by an independent committee.

Example of a table supplied to the DSMC: Mortality and Morbidity (mRS \geq 3) All patients Group B Group A **DELTA** ruptured DELTA unruptured Treatment-related (within 30 days) Strictly Possibly Aneurysm-related (> 30 days) Not related (> 30 days) This pattern will apply to mortality, morbidity, morbi-mortality and SAEs. **B.** Definitions **Adverse Event** Any procedural event (thromboembolic, hemorrhage, complication). During follow-up, any symptomatic event. During follow-up, any imaging finding secondary to investigation of symptom. Adverse Events will be categorized into: minor or moderate and serious **Serious Adverse Event** Results in death or is life threatening. Requires hospitalisation or prolongation of existing hospitalisation. Results in persistent or significant disability or incapacity or is otherwise considered medically significant by the investigator **End of study** Death

- No coils deployed during procedure or additional procedure

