B/ The use of the highest safely achievable proportion of 15-caliber coils, including Deltamaxx, the operator being unrestricted in the use of the coil he/she believes is appropriate at any time during the procedure using standard or adjunct techniques.

The aim of treatment is the complete angiographic exclusion of the aneurysm, or, as complete an exclusion from circulation as is feasible while minimizing risks of the procedure as per practice standards.

The interventionist and therefore the clinical and interventional research team cannot be blinded to the nature of the coils used. However, the imaging center (core lab) that will determine the success of the procedure will be blinded during its evaluation.

Although the mechanism evoked to support the potential benefit of 15-caliber coils is an increase in 'packing density', the trial does not require the use of a minimal number or length of coils of either nature, nor to reach a certain packing density. To attempt to introduce more coils, even after angiographic exclusion of the lesion, to increase packing density, could be seen as taking unjustified additional risks. The use of balloon assistance for coil deployment or stents deployed after coiling is authorized but will be recorded. Parent vessel occlusion concomitant to endosaccular coiling can be performed as long as it was not the procedure's primary intent.

Selection criteria

Inclusion criteria

- At least one ruptured or unruptured aneurysms with a dimension ≥4 mm and ≤12 mm (longest axis)
- For ruptured lesions, patients should be in WFNS grade < IV.
- The anatomy of the lesion is such that endovascular treatment is possible with both types of coils (not necessarily certain or probable)
- Patient is 18 or older
- Life expectancy is more than 2 years

Exclusion criteria

- Patients with planned treatment of an associated cerebral arteriovenous malformations
- When parent vessel occlusion, without simultaneous endosaccular coiling of the aneurysm, is the primary intent of the procedure
- Any absolute contraindication to endovascular treatment, angiography, or anaesthesia such as severe allergies to contrast or medications

Treatments

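### Appendix 3 defines morbidity as mRS 3 or more without an entry reference, an explicit separation from deaths, or a non-treatment row before day 30, so the treatment-related safety counts can be inflated equally in both arms

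*Combined protocol and SAP*

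**What the plan says.** Appendix 3 of the protocol (Safety) lists mortality, "Morbidity (mRS ≥ 3" and "Combined Mortality & Morbidity(M&M) (mRS ≥ 3 at 12 months" among the safety endpoints. Morbidity alone has no visit attached, and neither definition refers to the patient's mRS at entry or sets an upper limit on the score.

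The causality classes follow. One is "Strictly treatment related: any M&M associated with a procedural event or complication or hemorrage". The next is "Possibly related: any M&M occurring within 30 days". The third is "Not treatment related (> 30 days". The example table for the DSMC carries the row labels "Treatment-related (within 30 days) Strictly Possibly Aneurysm-related (> 30 days) Not related (> 30 days", and "This pattern will apply to mortality, morbidity, morbi-mortality and SAEs". Results are given for all patients and separately by rupture status, and an independent committee adjudicates the safety data.

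Elsewhere in the protocol:

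- **Section 2, Inclusion criteria:** "For ruptured lesions, patients should be in WFNS grade < IV". No selection criterion limits entry mRS.
- **Section 2, Table 1:** mRS is scheduled at entry, discharge, 6 months and 12 ± 2 months.
- **Section 2, Mortality:** deaths are classed as due to the illness, to coil embolization, or to neither, with no 30-day limit.
- **Section 2, Planned analyses:** follow-up neurological data are adjusted for baseline where this is possible.

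**The concern.** A safety count meant to show harm from coiling should not depend much on how disabled patients were before coiling. Here it can. Take a ruptured patient who enters at mRS 4 because of the bleed and leaves hospital at mRS 4 after an uneventful procedure. That patient meets the morbidity definition, and the table offers no row before day 30 other than Strictly or Possibly treatment-related. An unruptured patient with a stable mRS of 3 from an old condition is in the same position.

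Morbidity and combined morbidity-mortality also share one cut-off, so a reader of the 12-month tables cannot tell from the definitions whether deaths sit inside the morbidity line.

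This matters because the pilot is meant to verify safety and the DSMC advises on moving to the pivotal phase (Section 2, Pilot phase). The DSMC may also recommend changing or stopping the trial on safety data (Section 3, Day to day management).

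**Working it through.** The documents state no rate, margin or power for the safety endpoints, so there is no figure of the plan's own to reproduce. The check has two parts.

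**1. The definitions side by side**

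- *Entry status.* The morbidity definition is an absolute cut-off. Entry mRS is collected (Table 1) but the definition does not use it.
- *Deaths.* For the combined endpoint to include mortality, mRS of 3 or more must take in deaths. Morbidity has the same cut-off without an upper bound. Read at 12 months, the two definitions describe the same set of patients.
- *Attribution before day 30.* The available rows are Strictly and Possibly, both under treatment. The aneurysm-related and unrelated rows are tagged as later than 30 days. The Mortality paragraph of Section 2 has an illness-related class with no such limit, so the two schemes differ for early deaths.
- *Timing.* Table 1 has no 30-day mRS. Morbidity within 30 days will usually rest on the discharge score.
- *Presenting bleed.* The Strictly class names haemorrhage without saying whether the bleed that brought the patient in is excluded.

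**2. Size of the dilution (illustration; inputs assumed)**

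Let *b* be the share of patients counted at mRS 3 or more for reasons present at entry, equal in both arms. Let *t* be the rate of new morbidity, assumed 4% in one arm and 8% in the other. The counted rate is *p = b + (1 − b)t*.

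For *b* = 10%: p0 = 0.10 + 0.90 × 0.04 = 0.136 and p1 = 0.10 + 0.90 × 0.08 = 0.172. The risk ratio is 0.172/0.136 = 1.26, and 0.10/0.136 = 74% of the lower arm's count was present at entry.

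Power (two-sided 5%, normal approximation, *n* per arm, p̄ the mean of p0 and p1, wrong-direction rejections ignored) is

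Φ{[(p1 − p0) − 1.96√(2p̄(1 − p̄)/n)] / √[(p0(1 − p0) + p1(1 − p1))/n]}.

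With *n* = 282 and *b* = 10%: (0.036 − 0.0596)/0.0304 = −0.777, so power is 0.219.

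The planned full size is 282 per arm. The pilot of about 165 patients gives 165/2, or about 82 per arm.

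| b | Counted rates | Risk ratio | Present at entry, lower arm | Power, 282 per arm | Power, 82 per arm |
|---|---|---|---|---|---|
| 0% | 4.0% v 8.0% | 2.00 | 0% | 52% | 19% |
| 5% | 8.8% v 12.6% | 1.43 | 57% | 31% | 12% |
| 10% | 13.6% v 17.2% | 1.26 | 74% | 22% | 9% |
| 20% | 23.2% v 26.4% | 1.14 | 86% | 14% | 7% |
| 30% | 32.8% v 35.6% | 1.09 | 91% | 10% | 6% |

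The risk difference shrinks only by the factor 1 − *b* (4.0 points to 3.6 at *b* = 10%). Most of the loss in the ratio and in power comes from the added background.

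**The case against.** Several arguments on the other side have force.

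- **The word *occurring* can mean new onset.** A deficit already present at entry has not naturally occurred within the window, and an independent committee adjudicates. This stands as a possible reading. A reader might infer that such patients will certainly be filed as possibly treatment-related; the documents do not support that. But no rule states the new-onset reading, and the example table gives adjudicators no other row before day 30.
- **Deaths as morbidity is an inference.** The protocol never assigns death an mRS grade, and it lists mortality separately, so separation was probably intended. It would be too strong to say that morbidity cannot be read apart from mortality: at a common visit, survivors with mRS of 3 or more follow by subtraction. What remains is that the definitions do not say this and morbidity has no visit.
- **Coil-related harm is not hidden.** The DSMC also sees the Strictly row, the split by rupture status and the SAE counts. The calculation above describes one pooled count and does not give the power of those rows. This stands.
- **The background is unknown.** Entry disability after an acute bleed may resolve, so the share at 12 months need not equal the share at discharge. At pilot size power is about 19% even with no background. This stands.
- **Worsening from entry is a poor sole definition.** A ruptured patient who enters at mRS 4, has a procedural stroke and ends at mRS 3 or 4 would be missed. This stands, and it is why the absolute count should remain the main line.

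The baseline adjustment in Planned analyses is a partial answer. It concerns follow-up analyses and changes neither the endpoint nor the DSMC rows. The rupture split leaves entry disability within the ruptured group.

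**Conclusion.** The point holds as a gap in definition and attribution. Appendix 3 does not refer morbidity to entry status, gives it no visit, and does not separate it from the combined endpoint at 12 months. On a literal reading, the table counts disability present at entry as possibly treatment-related. The consequence is an inflated row in both arms and dilution of any true excess. Randomization, with minimization on rupture status, should balance the background, so there is no systematic bias between arms.

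The size cannot be stated for this trial. The fall in risk ratio from 2.0 to 1.26 at 10% background, and in power from 52% to 22% at 282 per arm, rests on assumed rates and on the literal reading. It shows direction and scale only. The primary efficacy endpoint is not affected. This is an inexpensive improvement to safety reporting and does not make the safety data unusable.

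**What to change.** In Appendix 3:

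1. Define morbidity as mRS 3-5 in survivors at a stated visit, mortality as death, and combined morbidity-mortality as either.
2. Keep the absolute count, by rupture status, as the main line. Add a second line counting only patients whose mRS of 3-5 is worse than their entry mRS.
3. State that morbidity or mortality within 30 days means new or worsened since entry, or associated with a procedural event. Procedural harm in a ruptured patient with a high entry score then still counts under Strictly. Say also whether the presenting bleed is excluded from the haemorrhage named in that class.
4. Allow aneurysm-related and unrelated attribution before day 30, and reconcile the classes with the death categories under Mortality in Section 2.

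The cost is appendix wording and one extra table line; entry mRS is already scheduled, so no new data are needed. The drawback is that the entry-referenced line is less informative in ruptured patients, whose entry score reflects the acute bleed. It should therefore stand beside the absolute count and not replace it.

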Patients allocated to caliber-15 coiling will preferably receive caliber-15 coils (perhaps including a caliber-15 framing coil (or not), as many Deltamaxx filling coils as safely achievable, but the procedure can be completed with caliber-10 or smaller finishing coils, in order to achieve as complete an occlusion as possible, keeping the procedure as safe as possible.

Patients allocated to caliber-10 coiling will preferably receive caliber-10 coils (perhaps including a caliber-10 framing coil, caliber-10 filling and finishing coils), once more to achieve as complete an occlusion as possible, keeping the procedure as safe as possible.

Both groups will receive platinum coils only. Balloon-assisted or stent-assisted coil embolization is permitted, but should be noted in the procedure CRF.

Technical freedom

The goal of the endovascular procedure is (as usual) to realize the most complete exclusion of the lesion that is judged to be possible, while keeping risks as small as possible, using the randomization algorithm's assigned embolization material. At any time during the procedure the interventionist is unrestricted in the use any device, technique or drug judged important to the safety and success of the endovascular procedure.

If a patient is randomized to 15-caliber coils but the operator prefers, for strong clinical reasons not initially thought of at the time of recruitment, not to deploy predominantly voluminous coils in this particular case, he should proceed using appropriate coils in the best interests of the patient. The converse is also true. In any such case, the operator details reasons on the endovascular treatment case report form. Analysis will be on an intention to treat and per-protocol basis.

Randomization

DELTA is designed with 1:1 randomization.

A minimization algorithm will be used whether the aneurysm is ruptured or unruptured and previously treated or not (major recurrence).

Type, frequency and duration of follow-up

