For the patients allocated to 15-caliber coils, the interventionists will have a choice to use 15-caliber coils only and/or other coils during the embolization procedure, in order to guaranty the same safety and immediate efficacy as the standard procedure. A study protocol deviation will be considered to have occurred if < 30% of coil length is 15-caliber coils. The initial technical success or failure of the procedure will be determined after treatment by the adjudication committee by reviewing core lab independent result of procedural angiogram and coils uses as recorded in the data collection sheets.

Mortality

The death rate will be recorded for the intent-to-treat analyses. It will be obtained by dividing the number of deaths by the number of patients in each group. Mortality will be categorized as being a/related to the illness, b/ related to coil embolization or c/ unrelated.

Adverse events

Adverse events will be recorded immediately after the procedure and during the 12-month follow-up period. Serious adverse events (SAEs), those that are life threatening, leading to hospitalizations or prolonged hospitalizations, as well as unexpected events will all be reported within 48 hours to the data coordination centre that will transmit the information to the DSMC. The number and severity of all reported adverse events will be recorded for each patient and for each treatment group.

Morbidity

The number and the severity of morbid events per patient will be recorded for each patient. The modified Rankin scale will be measured at follow-up appointments. This scale classifies the patients according to their neurological outcome.³⁹

Sample size

A decrease in the recurrence rate from 33 to 20% would be clinically significant. Based on Fisher's Exact test, a total sample size of 512 patients would allow detecting such a difference with a power of 90% and an alpha error of 0.05 (Table 2). A sample size of 564 patients for DELTA is sufficient to detect a decrease in the recurrence rate from 33 to 20% with an alpha error of 5% and a beta error of 10%, allowing 10% of losses at determination of the primary endpoint

Table 2: Log Rank Survival Power Analysis - Simple - Primary Hypothesis

Two Independent Proportions (Null Case) Power Analysis
Numeric Results of Tests Based on the Difference: P1 - P2
H0: P1-P2=0. H1: P1-P2=D1<>0. Test Statistic: Fisher's Exact test

	Sample	Sample	Prop H1	Prop					
	Size	Size	Grp 1 or	Grp 2 or	Diff	Diff			

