Descriptive statistics will be done on demographic variables and pre-operative and peri-operative data to compare the two groups at baseline. Means, standard deviations and range will be presented for quantitative variables and frequency tables for categorical variables. Those statistics will be broken down by treatment arm. Comparability of the groups will be assessed through independent ANOVAs (quantitative data) or Mantel-Haentzel and chi-square tests (categorical data). For the pilot phase, the number of patients with satisfactory immediate angiographic results, as well as the mean packing density, will be compared between the 2 groups. The primary outcome of the pivotal phase, recurrence rates (for both intent-to-treat end per-protocol populations) will be compared between groups through a z-test for independent proportions at 6 months and 12 months. Secondary outcomes and safety data will be compared between groups through independent t-tests (quantitative variables) or chi-square statistics (categorical data). The analyses of neurological data at follow-up will control for baseline data when possible (for tests done before discharge and at follow-up) using logistic regression, ANCOVA or Cox regression multivariate models. All tests will be interpreted with adjustment for the interim analysis to have the 0.05 level of confidence at 12 month only. Finally, a logistic regression will be used to find variables capable of predicting recurrences. The method planned is a stepwise forward with alpha < 0.05 to enter a predictor. Possible predictors include the type of the aneurysm, location, size of the aneurysm, size of the neck of the aneurysm as well as other baseline characteristics.

Pilot phase

The pivotal trial will be preceded by a pilot phase of approximately 165 patients designed to verify the feasibility of the coiling strategy, compliance to treatment group allocation, the safety of an 15-caliber platinum coil embolization strategy, recruitment rates, and the capacity to improve packing density with a standardized effect size (E/S) of 0.60, with a power of 95% and a two-sided alpha error of 0.05 (assuming the packing density of the control group will be approximately 25%). The data will be reviewed and analyzed by the DSMC and recommendations will be forwarded to the Steering Committee regarding continuation into the pivotal phase of the study.

Protection against bias

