For ruptured aneurysms, the physician will explain the treatment options including surgery to the patient and relatives. If endovascular treatment is to be offered, the physician will explain the potential benefits of using voluminous coils in terms of reducing the recurrence rate. Following verification that inclusion and exclusion criteria are met, the consent form and voluntary nature of participation into the study will be explained to the patient and relatives. The patient and family will be offered to sign the consent form. At this time, the recruitment form is filled and randomization can proceed online.

7. Randomization is automatic after the registration form is entered.

- 8. Elective patients are scheduled for treatment (within 1-2 months). Ruptured cases are treated as soon as possible as generally done. Images are sent to the coordinating centre.
- 9. For all patients, a procedure form is completed following treatment. Pre and final images, as well as 24 hour or at discharge CT scan, are sent to the coordinating centre.

 Discharge assessment form completed at the time of discharge.
- 10. Severe adverse events are entered online or faxed within 48 hours to the coordinating centre. The coordination center will transmit the information to the clinical adjudication committee which will relay it to the DSMC. These events include haemorrhages, strokes related to the aneurysm, deaths, or further treatments of aneurysm.
- 11. All patients will be followed at 6 and 12 months. Follow-up visits are crucial to assess any change in medical condition and to answer questions.
- 12. For all patients, follow-up visits at 6 and 12 months and vascular imaging 12 (±2) months. Follow-up angiography, catheter or non-invasive, is required. Images are sent to the coordination centre.

Centre requirements

- 1. Participating centres will be regional referral centre for the treatment of intracranial aneurysms. They will have demonstrated a large experience in endovascular treatment of aneurysms (at least 100 patients treated with safety records within acceptable limits (< 8% overall treatment-related complications; < 4% poor outcome at follow-up).
- 2. The names of operators in each centre should be submitted to the coordinating centre. The years of experience and number of aneurysms treated will be kept in a confidential centre log.

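### Appendix 3 ends the study for randomised patients who receive no coil, against 12-month follow-up of all patients, and no rule says how they count in the intention-to-treat primary comparison

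*Combined protocol and SAP*

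**What the plan says.** Appendix 3, under Definitions, gives three events that end the study: death, "No coils deployed during procedure or additional procedure", and completion of the 12-month follow-up.

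Other parts of the same document cover the same patients:

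- Section 4, DELTA treatment plan, item 7: "Randomization is automatic after the registration form is entered". Item 8 then schedules elective patients for treatment within 1-2 months.
- Items 11 and 12 of that plan: "All patients will be followed at 6 and 12 months", and "For all patients, follow-up visits at 6 and 12 months and vascular imaging 12 (±2) months". Neither makes an exception for uncoiled patients. Section 2, Duration of the trial, likewise gives every patient 12 months of follow-up.
- Section 2, Technical freedom: "Analysis will be on an intention to treat and per-protocol basis". Planned analyses, on the pivotal primary outcome: "recurrence rates (for both intent-to-treat end per-protocol populations) will be compared between groups".
- Section 2, Mortality, on the death rate: "It will be obtained by dividing the number of deaths by the number of patients in each group".
- Appendix 3, Safety, sets the scope of endpoint assessment as "For all DELTA patients" and defines combined mortality and morbidity by mRS at 12 months.

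Where follow-up imaging is absent, Section 2 (Primary endpoint) and Appendix 3 leave other treatment failures to an adjudication committee. They give four examples: haemorrhage, retreatment, mass effect, and morbidity or mortality that prevents follow-up. Failure to place a coil is not among them, but the list is introduced as examples and is therefore open.

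**The concern.** A no-coil procedure can only become known after allocation. If it ends the study, a post-randomisation event decides who is followed, which is what an intention-to-treat analysis is meant to prevent.

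Two things are at stake.

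- **Data.** Events during the procedure and up to discharge are still captured. Later deaths, later serious adverse events and the 12-month mRS are not, if a site follows Appendix 3. Another site following Section 4 would collect them, so the same kind of patient could be handled differently across centres.
- **The primary comparison.** Intention to treat fixes who is in the denominator. It does not say whether a never-coiled patient is a failure, a non-failure or missing. The answer would be reached case by case, with little follow-up information to draw on.

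No-coil cases are foreseeable. The selection criteria ask only that coiling be possible with the coil types, not that success be likely.

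**Working it through.** **1. The plan's own figures.** Section 2, Sample size, gives 256 per arm (512 in total) for 33% against 20%, two-sided Fisher's exact test, alpha 0.05, 90% power, and 564 after a 10% loss allowance. Exact Fisher power at 256 per arm is 0.903 (Table 2: 0.9009), and 512 × 1.10 = 563.2, rounded up to 564. Both figures reproduce and neither is in dispute. At 282 per arm less 10%, about 254 are evaluable (282 × 0.9 = 253.8).

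**2. Set-up.** Planned analyses names a z-test for proportions, so the powers in step 3 are exact powers of the two-sided pooled z-test at 254 per arm, alpha 0.05. Let p be the failure rate among coiled patients (0.20 in the 15-caliber arm, 0.33 in control) and q the no-coil rate. If no-coil patients count as failures, the arm's failure rate is

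q + (1 − q) × p.

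Example with q = 0.05 in the 15-caliber arm and 0.02 in control: 0.05 + 0.95 × 0.20 = 0.2400; 0.02 + 0.98 × 0.33 = 0.3434; difference 0.1034.

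The documents give no value for q. Every rate below is an assumption.

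**3. Results.**

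| No-coil rate, 15-caliber / control | Handling | Difference (points) | Power |
|---|---|---|---|
| any | dropped, 254 per arm remain | 13.0 | 91.7% |
| 2% / 2% | dropped on top of the 10% loss, 249 per arm | 13.0 | 91.2% |
| 1% / 1% | failures | 12.9 | 90.7% |
| 2% / 2% | failures | 12.7 | 89.6% |
| 5% / 5% | failures | 12.35 | 86.2% |
| 3% / 2% | failures | 11.9 | 85.2% |
| 5% / 2% | failures | 10.3 | 73.1% |
| 2% / 5% | failures | 14.75 | 95.9% |

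Rates of 1%, 2% and 5% of 564 are about 6, 11 and 28 patients.

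**4. Variations.** In step 3 the 10% loss falls on all patients alike. If it falls on coiled patients only, with no-coil counts left random, power is 89.4% (2%/2%), 85.6% (5%/5%), 70.5% (5%/2%) and 96.2% (2%/5%). The pattern is unchanged.

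With Fisher's exact test (0.900 at 254 per arm with no such patients) and no-coil patients only in the 15-caliber arm, at 1% to 5%:

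- counted as failures: difference 12.2 down to 9.0 points, power 0.855 down to 0.577;
- counted as non-failures: difference 13.2 up to 14.0 points, power 0.910 up to 0.942.

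With the data unchanged, the counting rule alone moves the expected difference by 14.0 − 9.0 = 5.0 points at a 5% rate.

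**The case against.** The case for treating this as minor has four parts.

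- **Adjudication already covers these patients.** The committee is to decide the endpoint for every patient, and its list of failures without imaging is open. This stands in part: the committee may call a no-coil case a failure. Nothing requires it to, and stopping follow-up removes the information on later haemorrhage, retreatment or mass effect that it would use.
- **The item does not tell sites to stop contact.** It is one line in a definitions list, the working instructions are in Section 4, and its mention of an additional procedure suggests that one failed session need not end participation. The last point is a fair reading. Even so, once no coil has been placed at any procedure, the item ends the study, and the exception is stated nowhere else. Two rules that cannot both be followed need reconciling.
- **An arm difference is unsupported.** Operators may use either caliber in either arm, and the anatomy must allow both coil types. This stands: a difference is possible but not established, and the 5% against 2% rows show sensitivity, not an expectation.
- **Equal rates do little, and counting as failures is a choice.** Both stand. At 1% or 2% in each arm, power stays close to 90%, and the loss allowance could absorb a few dropped patients. Counting never-coiled patients as failures is one defensible convention among several.

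None of this removes the contradiction or supplies a rule.

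**Conclusion.** The concern holds. The end-of-study item contradicts the follow-up schedule and undercuts the intention-to-treat analysis, the all-patient mortality denominator and the 12-month safety assessment. The handling of these patients in the primary comparison is unstated.

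The certain consequence, if a site applies Appendix 3, is the loss of late safety and functional outcomes for a group selected after randomisation. The effect on the primary result depends on rates the documents do not give. At equal rates of 1% to 2% it is negligible; at 5% in both arms counted as failures, power falls to 86.2%. Only an arm difference moves the result materially, and it could do so in either direction. The point deserves correction, but it does not undermine the design.

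**What to change.** 1. Delete the no-coil item from the End of study list in Appendix 3, so that it agrees with Section 4, items 11 and 12.
2. State that every randomised patient is followed to 12 (±2) months for vital status, serious adverse events and mRS, whether or not a coil was placed. Section 2 already allows telephone collection.
3. Keep never-coiled patients in the intention-to-treat denominator, and fix in advance how they count for the primary endpoint: for example as failures, with a sensitivity analysis that excludes them. Settle this before anyone sees outcome data by arm.
4. Report the number of never-coiled patients per arm under initial technical success.

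The cost is a few lines of text and a 12-month contact for perhaps 6 to 28 of 564 patients at the assumed 1% to 5%. If these patients count as failures, the observed effect may be slightly less favourable.
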